Non-inferiority study of immediate or delayed provisionalization at posterior healed sites using NobelParallel™ CC implants

STUDY PURPOSE AND RATIONALE

Dental implants are a widely used treatment option for the replacement of lost teeth due to trauma or oral diseases. The original protocol for placement of dental implants in edentulous spaces in the maxilla or the mandible was introduced more than thirty years ago and called for a two-stage approach, i.e., surgical placement of submerged dental implants and subsequent uncovering with abutment connection, prosthesis fabrication and functional loading approximately 6 months after (Brånemark et al., 1983). Today, the time between surgery and loading in a two-stage protocol has been commonly abbreviated to 3-4 months, while immediate implant provisionalization has emerged as a reliable and predictable option in cases of adequate osseous support, having similar survival and success rates to the two-step procedure (Esposito et al., 2009). Comparison of histological healing has demonstrated no significant differences in bone to implant contact between implants surgically placed according to a two-stage protocol and those immediately provisionalized (Piattelli et al., 1993). However, Esposito et al. (2009) also noted a substantial variability among the clinical protocols used in the studies carried out so far, and concluded that additional well-designed randomized controlled trials (RCTs) are needed to fully appreciate the clinical outcomes of immediate and early loading protocols.

The design of dental implants is a subject of continuous improvement, and implant manufacturers regularly introduce new products the use of which may result in accelerated soft and hard tissue healing, increased initial implant stability, and enhanced esthetic outcomes. The purpose of this randomized, controlled trial is to compare treatment outcomes when using a newly-introduced dental implant (NobelParallel™ CC) in a one-stage or a two-stage protocol. This new implant has the same titanium oxide surface coating (TiUnite®) and the same design principles of the parallel-walled NobelSpeedy Groovy™ implants, and an internal conical connection. The implant is marketed under the premarket notifications K050406 and K073142 (510 (k), Food and Drug Administration).

SUMMARY OF STUDY PURPOSE

To compare two loading protocols using the new implant (NobelParallel™ CC) in posterior healed sites in two treatment arms: one in which the implant will be immediately provisionalized at the time of surgery, and another where the provisional crown will be delivered 3 months after the surgical procedure.

STUDY DESIGN AND STATISTICAL PROCEDURES OVERVIEW

This is a non-inferiority study of 12-month duration comparing the two treatment arms described above. Eligible patients with edentulous spaces at the maxillary or mandibular premolar/molar areas will be randomized to either an immediate provisionalization or a delayed provisionalization treatment arm. Patients in both treatment arms will receive their final fixed restoration at 4 months after surgery. The primary outcome of the study will be the radiographically assessed alveolar bone level change at the mesial and distal surface of the implant at 6 and 12 months after surgical placement. Secondary outcomes will include implant survival,

volumetric soft tissue changes, peri-implant probing depth, and implant stability by resonance frequency analysis.

POWER CALCULATIONS AND STATISTICAL ANALYSIS

Determination of sample size was based on anticipated differences in the primary outcome between the two treatment arms at 6 months (change in alveolar level from the time of implant placement). Based on similar data published in the literature (Esposito et al., 2013), we calculated with 1 mm bone remodeling in one treatment arm, and 1.5 mm bone remodeling in the second arm (i.e., expected mean difference between the two arms amounting to 0.5 mm). With a common standard deviation in both arms of 0.6 mm, the two-tailed effect size for a Student t-test (Cohen's d) amounts to 0.8333 mm. For an alpha error of 0.05 and power of 0.80, a total of 48 individuals in both arms is required for a two-tailed hypothesis. Thus, our plan is to enroll 50 individuals into the study.

Differences in the primary and secondary outcomes between the two treatment arms will be calculated using t-test for unmatched samples, after checking for data normality. Additional analyses will include regression models in which insertion torque (a measure of primary implant stability at the time of surgical placement) will be also used as a covariate along with treatment group allocation.

STUDY PROCEDURES

Eligible participants (i.e., adults ≥ 18 years old in need of a dental implant at a posterior maxillary or mandibular region) who have been referred for dental implant treatment at the Clinics of the College of Dental Medicine will be approached by the study investigators and the aims of the study will be explained. Signed informed consent will be obtained.

All patients will be referred for limited field cone beam computer tomography to assess presence of adequate bone volume at the area of interest, according to standard clinic protocol. Alginate impressions will be obtained to fabricate diagnostic stone casts. A vacuum-formed stent will be manufactured in the laboratory to offer fixed reference points for longitudinal probing measurements, and a radiographic stent using polyvinyl siloxane interocclusal record material will allow standardized positioning of the radiographic holder to obtain periapical radiographs with the same projection geometry.

At the day of surgery (baseline), a computer-generated sequence will assign patients to either the one-stage or the two-stage treatment arm. In both arms, the implant will be placed flush with the bone crest, after flap elevation, according to standard treatment protocol. A periapical radiograph will be obtained immediately after completion of surgery.

Patients in the one-stage group will receive a temporary acrylic crown manufactured chair-side at the same visit. Care will be taken to relieve the crown from occlusal and laterotrusive contacts. The distance from the soft tissue margin to the occlusal stent will be measured using a periodontal probe at six sites around the implant (mesiobuccal, midbuccal, distobuccal, mesiolingual, midlingual and distolingual) at the time of post-surgical follow-up, 1-2 weeks after surgery.

At three months after implant surgery, patients in the two-stage group will have the implant uncovered after punching the oral mucosa, according to standard protocol. An acrylic temporary crown will be delivered. Soft tissue margin assessments measurements will be carried out, as described above, will be carried out at the time of post-surgical follow-up, 1-2 weeks after surgery.

At four months after implant surgery, patients in both arms will have a final fixture level impression according to standard protocol for fabrication of the final implant supported restoration (a full contour Zirconia abutment crown with an angulated screw channel), which will be delivered approximately 2 weeks later. Resonance frequency analysis measurements will be obtained to determine implant stability using an Ostell™ device. After delivery of the final restoration, a periapical radiograph will be obtained, soft tissue margin measurements will be carried out as described above, and peri-implant probing depths will be assessed at the same six sites. An alginate impression will also be obtained to produce a stone cast to be used in volumetric measurements.

At seven months after implant surgery, patients in both treatment groups will return for a follow up visit to reinforce oral hygiene and will receive oral prophylaxis.

At twelve months after implant surgery, patients in both treatment groups will return for a follow up visit to reinforce oral hygiene and to receive oral prophylaxis. Resonance frequency analysis measurements will be obtained to determine implant stability using an Ostell™ device. A periapical radiograph will be obtained, soft tissue margin measurements will be carried out as described above, and probing depths will be assessed at the same six sites around the implant. An impression will be obtained to produce a cast to be used in volumetric measurements. The 12-month examination will conclude the study visits.

Research procedures

1. Radiographic measurements of alveolar bone level mesial and distal to the implant (at baseline, four months and 12 months) will be carried out using the MIPACS software. The implant platform will be the reference point. Note that although the measurements will be carried out for the purposes of the study, periapical radiographs after completed surgery, at the time of delivery of the final restoration, and at 12-months post-surgery are standard protocol in implant dentistry. Thus, the study does not require any additional exposure to radiation beyond what is considered the standard of care.
2. Measurements of soft tissue margin from a vacuum-formed stent at 6 sites per tooth (obtained at the day the provisional crown is delivered, i.e. at the post-operative visit 1-2 weeks after implant placement in the one-stage treatment arm, or at the post-operative visit 1-2 weeks after implant uncovering in the two-stage arm).
3. Probing depth measurements around the implant (at 4 and 12 months).
4. Volumetric assessments, based on digitally super-imposed casts (obtained at screening, 4 months and 12 months).
5. Resonance frequency analysis measurements using a Ostell™ device (at 4 and 12 months). These are non-invasive measurements of implant stability.

STUDY DRUGS

N/A

STUDY INSTRUMENTS

The NobelParallel™ CC implant is a new implant that has the same titanium oxide surface coating (TiUnite®) and a parallel-wall body design similar to the NobelSpeedy groovy™ and a conical internal connection. Both the implant and its prosthetic components have regulatory clearance [510(k)] by the Food and Drug Administration.

ADDITIONAL DATA COLLECTION

We will collect and review standard medical and dental history forms to confirm eligibility (age 18 years or older, participants who are systemically healthy or have controlled common systemic conditions, not pregnant, non-smoking or smoking <10 cigarettes/day, have no parafunctions or excessive occlusal forces, are not currently under orthodontic therapy, and have a stable occlusion). Intraoral photographs will be obtained for documentation purposes.

STUDY SUBJECTS

We will recruit 50 subjects among those referred to the College of Dental Medicine for tooth replacement using a dental implant in a posterior maxillary or mandibular region (premolar/molar area).

ADDITIONAL INCLUSION CRITERIA

Age 18 or older

Healed extraction sockets (extraction carried out at least 3 months prior to recruitment)

Implant site free of infection

Systemically healthy patients or with controlled common systemic conditions

Adjacent teeth present both mesially and distally to the implant site

EXCLUSION CRITERIA

Pregnancy or intent to be pregnant over the next 12 months

Current smoking exceeding 10 cigarettes/day

Parafunctional habits/ excessive occlusal forces

Current orthodontic therapy

Uncontrolled hypertension (blood pressure over 160/100) or poorly-controlled diabetes (HbA1c>8%).

RECRUITMENT

Potential participants will be approached by the study investigators and the scope and the procedures of the study will be thoroughly explained. Eligible individuals willing to participate will provide informed consent.

CONFIDENTIALITY OF THE DATA

Participants will be assigned individual study numbers that will be used to link all collected study data. All endpoint devices used for data collection will be password-protected and encrypted. PHI/PII data and all other study data will be stored in a secure, certified database. The following individuals/ institutions/ representatives will have access to the records: the Principal Investigator and co-investigators, the FDA, the Department of Human Health and Human Services, the Columbia University/New York Presbyterian Hospital, and the Institutional Review Board. Absolute confidentiality cannot be guaranteed because of potential need to share this information with the above parties. Only aggregate findings of this study will be published.

POTENTIAL CONFLICT OF INTEREST

The study is an investigator-initiated randomized controlled trial, where the Principal Investigator serves as the Sponsor-Investigator. The study is partially supported by a grant provided by the implant manufacturer (Nobel Biocare). None of the investigators have any financial interest in the company or have served as paid consultants.

LOCATION OF THE STUDY

All study procedures will take place at the Clinics for Post-doctoral Periodontics and Post-doctoral Prosthodontics, College of Dental Medicine, Columbia University Medical Center, Vanderbilt Clinic, 9th floor.

POTENTIAL RISKS

Study related risks: The overall success of dental implants exceeds 95%. Risks associated with the study are identical to those associated with surgical implant placement and include soreness, discomfort, pain, infection, nerve damage and implant failure.

Protection against risks: Implants will be placed and restored by post-doctoral residents who are proficient in the surgical and restorative aspects of implant dentistry, under faculty supervision. Patients will receive post-operative antibiotic and analgesic coverage, according to standard clinical protocol.

POTENTIAL BENEFITS

Patients will have the costs associated with implant surgery and provisional restoration waived, as these will be covered by funds provided by the implant manufacturer (NobelBiocare).

ALTERNATIVE THERAPIES

- 1) not to replace the missing tooth

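### The trial is sized on a 6-month bone-level change, but no radiograph is scheduled at 6 months, and neither the deciding timepoint nor the mesial/distal rule is stated

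*Combined protocol and SAP*

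**What the plan says.** In the protocol's Study Design and Statistical Procedures Overview, the primary outcome is "radiographically assessed alveolar bone level change at the mesial and distal surface of the implant at 6 and 12 months after surgical placement". In Power Calculations and Statistical Analysis, the sample size rests on "anticipated differences in the primary outcome between the two treatment arms at 6 months": 1 mm of remodeling in one arm against 1.5 mm in the other. The variability input is given as "With a common standard deviation in both arms of 0.6 mm". With two-sided alpha 0.05 and power 0.80 this leads to 48 patients, with 50 to be enrolled. The analysis is one sentence: "Differences in the primary and secondary outcomes between the two treatment arms will be calculated using t-test for unmatched samples", after a normality check.

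Study Procedures gives the imaging schedule:

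- At surgery: "A periapical radiograph will be obtained immediately after completion of surgery".
- At the final restoration (impression at four months, delivery about 2 weeks later): "After delivery of the final restoration, a periapical radiograph will be obtained".
- At 7 months: "At seven months after implant surgery, patients in both treatment groups will return for a follow up visit to reinforce oral hygiene", plus prophylaxis. No film is listed.
- At 12 months: a periapical film.

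Research Procedures, item 1, confirms this: "Radiographic measurements of alveolar bone level mesial and distal to the implant (at baseline, four months and 12 months". The same item, and the section on radiation, state that the study adds no radiographic exposure beyond standard care.

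**The concern.** The outcome definition and the measurement schedule disagree on when the early bone-level change is observed, and the sample size depends on the timepoint that is never imaged. As scheduled, the 6-month comparison cannot be carried out, and the stated 80% power belongs to it.

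Two further matters are open. Two primary timepoints are named, with no statement of which decides, whether both must succeed, or how alpha is shared. Bone level is read at two surfaces per implant, while the unpaired t-test needs one value per patient, and no rule says how that value is formed. With both choices open, the deciding timepoint and the surface summary could be picked after the data are seen. In a trial described as non-inferiority, it would then be unclear which estimate carries the conclusion.

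**Working it through.** **Step 1. Outcome timepoints against scheduled films.**

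| Time after surgery | Named in primary outcome | Used for sample size | Bone-level film scheduled |
|---|---|---|---|
| 0 (after surgery) | reference for change | reference for change | yes |
| about 4 to 4.5 months | no | no | yes |
| 6 months | yes | yes | no |
| 7 months | no | no | no |
| 12 months | yes | no | yes |

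The cone beam scan is taken before surgery to assess bone volume and cannot supply a change from placement. Scheduled 6-month films: 0 of 50 patients.

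**Step 2. Reproduce the plan's figure.** Inputs from the sample-size section: difference 1.5 − 1.0 = 0.5 mm, SD 0.6 mm, two-sided alpha 0.05. Equal allocation is assumed. The standardised difference is d = 0.5/0.6 = 0.833. Power comes from the noncentral t distribution with 2n − 2 degrees of freedom and noncentrality d·√(n/2):

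- 23 per arm: 78.9%
- 24 per arm: 80.7%, so the total of 48 reproduces
- 25 per arm (50 enrolled, no loss): 82.3%

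The arithmetic is sound; it applies to a timepoint that is not imaged.

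**Step 3. Do the inputs carry over to an imaged timepoint?** The delayed arm receives its provisional crown at 3 months. Time with a crown in place, immediate against delayed arm:

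- delivery film: about 4.5 against 4.5 − 3 = 1.5 months
- a true 6-month film: 6 against 6 − 3 = 3 months
- 12-month film: 12 against 12 − 3 = 9 months

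The contrast between arms may therefore differ across these times, and the documents give no difference or SD for either imaged one. To show how much this matters, the same test at 25 per arm with assumed inputs:

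| Difference (mm) | SD (mm) | Power |
|---|---|---|
| 0.5 | 0.5 | 93.4% |
| 0.5 | 0.6 (plan's inputs) | 82.3% |
| 0.5 | 0.7 | 69.7% |
| 0.5 | 0.8 | 58.1% |
| 0.4 | 0.6 | 63.7% |
| 0.6 | 0.6 | 93.4% |

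**Step 4. What the 0.6 mm describes.** The plan does not say whether it is the SD of one surface or of a patient-level value. If it is per surface and the two changes are averaged, with assumed within-implant correlation r, the SD becomes 0.6·√((1 + r)/2). With a 0.5 mm difference and 25 per arm:

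| r | SD of the mean (mm) | Power |
|---|---|---|
| 0.9 | 0.585 | 84.2% |
| 0.7 | 0.553 | 87.9% |
| 0.5 | 0.520 | 91.5% |
| 0.3 | 0.484 | 94.7% |

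If 0.6 mm already describes the patient average, 82.3% stands.

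All of these are powers for a two-sided test of difference. The plan states no non-inferiority margin, so no non-inferiority power can be computed.

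**The case against.** The strongest reply is that 6 months is a loose label for the early film. The 12-month component is fully imaged and an early film exists about 6 − 4.5 = 1.5 months before the stated time, so the repair would be a label correction and a check of the inputs. That reading is possible. It does not remove the problem: the 6-month wording appears in both the outcome and the sample-size text, and Step 3 shows why inputs for 6 months need not hold at the delivery film.

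Second, the illustrative powers use values not in the documents and fall on both sides of 80%, so they demonstrate no loss. This is correct. They show sensitivity to the inputs, not that the trial is underpowered.

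Third, the plan counts individuals, gives one mean per arm and uses an unpaired t-test, which together imply one value per patient. This also largely stands. What is missing is which summary is used and whether 0.6 mm applies to it; alone, that would be a request for clarification.

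Fourth, the absent margin is a separate defect and should not add weight here. Agreed: the contradiction between outcome and schedule is enough on its own.

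**Conclusion.** The concern holds and must be fixed. The primary outcome's 6-month component, which is the sole basis for the sample size, has no scheduled measurement in any patient. The timepoint hinted at as leading is thus the one without data, and no hierarchy is written down. The total of 48 is arithmetically correct but does not give the power of any comparison shown to be available. Whether actual power is above or below 80% cannot be determined from the documents; the range of 58.1% to 94.7% rests on assumed differences, SDs and correlations, on 25 analysable patients per arm, and on a difference test. The finding assumes that the visit text is complete, which the measurement list and the two radiation statements support. The missing surface rule is a companion gap on which the finding does not depend.

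**What to change.** Reconcile the outcome definition with the film schedule:

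1. Name one already-imaged timepoint, delivery of the final restoration or 12 months, as the single primary endpoint, and make the other secondary. The choice is the investigators', but the two are not interchangeable, since time under a crown in the delayed arm differs (about 1.5 against 9 months). The rationale should say which question is meant. If the 6-month label was intended for the early film, correct it.
2. Define the value per patient as the mean of the mesial and distal changes from the post-surgical film. Another summary would also close the gap if fixed in advance; the mean is the simple choice.
3. Replace the 6-month wording in both the outcome and the sample-size text.
4. State whether the 0.5 mm difference and 0.6 mm SD apply at the chosen timepoint and to the averaged value. The section already cites a systematic review for its remodeling figures; what is needed is the timepoint and unit to which those figures refer. If they do not apply, restate the power at 50 patients.

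No extra film, visit or patient is required. The cost is the work of re-justifying the inputs, and possibly having to report a power below 80%.

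### The trial is labelled non-inferiority but has no margin, direction or confidence-bound rule, and its 80% power is for detecting a 0.5 mm difference

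*Combined protocol and SAP*

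**What the plan says.** The title reads "Non-inferiority study of immediate or delayed provisionalization at posterior healed sites", and the Study Design and Statistical Procedures Overview repeats the label: "This is a non-inferiority study of 12-month duration comparing the two treatment arms described above".

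The section Power Calculations and Statistical Analysis describes something else. It begins "Determination of sample size was based on anticipated differences in the primary outcome between the two treatment arms at 6 months". It assumes "1 mm bone remodeling in one treatment arm, and 1.5 mm bone remodeling in the second arm", without naming the arms, and describes the result as the "expected mean difference between the two arms amounting to 0.5 mm". The SD is 0.6 mm in both arms. It concludes "For an alpha error of 0.05 and power of 0.80, a total of 48 individuals in both arms is required for a two-tailed hypothesis", and 50 patients are to be enrolled. Outcome differences "will be calculated using t-test for unmatched samples, after checking for data normality"; supplementary regression models add insertion torque as a covariate.

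Research procedures, item 1, lists "Radiographic measurements of alveolar bone level mesial and distal to the implant (at baseline, four months and 12 months". No section of the document gives a non-inferiority margin, names the arm that must be shown non-inferior, or gives a rule comparing a confidence limit with a margin.

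**The concern.** A non-inferiority conclusion needs three things fixed in advance: which arm is on trial, how much worse it may be, and which confidence limit must exclude that amount. None is present. A two-sided t-test addresses the hypothesis of no difference. Failing to reject that hypothesis does not show that the new approach is not unacceptably worse, and the plan does not say how a non-significant result would be read.

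The 0.5 mm cannot simply be taken as the margin, because the plan presents it as the difference it expects to see. If the immediate arm is the one expected to lose 1.5 mm, the plan anticipates a deficit equal to that margin. If it is the delayed arm, the plan anticipates that immediate treatment is better. The text does not say which.

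Without a rule set beforehand, either a non-significant p-value gets read as success, in which case the risk of accepting a worse arm is uncontrolled and grows as patients are lost, or a margin is chosen after the data are seen.

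**Working it through.** **Inputs from the power section.** Means 1.0 and 1.5 mm (difference 0.5 mm), SD 0.6 mm, two-sided alpha 0.05, power 0.80, total 48, enrolment 50.

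**Assumed, because not stated.** 1:1 allocation; non-inferiority tested at one-sided 0.025; margins of 0.5, 0.4 and 0.3 mm and evaluable numbers below 25 per arm, all for illustration.

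**1. The plan's own figure.** d = 0.5/0.6 = 0.8333. With n per arm, SE = 0.6 × √(2/n), and power comes from the noncentral t distribution with noncentrality 0.5/SE and 2n − 2 degrees of freedom.

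- n = 24: SE = 0.6 × √(2/24) = 0.1732; noncentrality 0.5/0.1732 = 2.887; power 0.807. Total 48, an exact match.
- n = 25: SE = 0.6 × √(2/25) = 0.1697; noncentrality 2.946; power 0.823.

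The 48 is therefore the number needed to detect a 0.5 mm difference.

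**2. Power for non-inferiority.** Let Δ be mean bone loss, immediate minus delayed, and M the margin. Non-inferiority is shown if the upper limit of the two-sided 95% CI for Δ lies below M. The noncentrality is (M − Δ)/SE. With Δ = 0:

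| Margin M | Power, 25 per arm | Total evaluable for 80% power |
|---|---|---|
| 0.5 mm | 82.3% | 48 |
| 0.4 mm | 63.7% | 74 |
| 0.3 mm | 41.0% | 128 |

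At M = 0.5 mm and Δ = 0 the noncentrality is the same as in step 1, so the two calculations coincide.

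Losses at M = 0.5 mm, Δ = 0: 24 per arm 80.7%; 24 v 23, 79.8%; 22 per arm 77.0%; 20 per arm 72.8%. If the SD at the analysed visit were 0.7 mm (assumption), 25 per arm would give 69.7%.

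Under the plan's own expected difference, with M = 0.5 mm and 25 per arm:

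- Immediate arm worse (Δ = +0.5): M − Δ = 0, so power equals alpha, 2.5%.
- Delayed arm worse (Δ = −0.5): M − Δ = 1.0 mm, and power exceeds 99.9%.

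**3. If p > 0.05 were read as non-inferiority.** With the immediate arm truly 0.5 mm worse, the chance of accepting it is one minus the power of the t-test:

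- 25 per arm: 1 − 0.823 = 0.177. A simulation of 200,000 trials gave 0.176.
- 20 evaluable per arm: 1 − 0.728 = 0.272.

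The confidence-interval rule with a 0.5 mm margin holds this probability at 0.025 for either number.

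**4. Width of the interval.** With 25 per arm the 95% half-width is 2.011 × 0.1697 = 0.341 mm. A result against the immediate arm that just misses significance has an observed difference of about 0.34 mm and an upper limit of about 2 × 0.341 = 0.68 mm, beyond the 0.5 mm used in the plan.

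**5. Visits.** The calculation is set at 6 months. The overview names 6 and 12 months as primary; radiographic measurements are listed for baseline, four and 12 months. The powered comparison has no scheduled measurement, and 12 months is the only visit that is both primary and radiographed.

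**The case against.** The strongest reply is that the trial may be the right size. The same 48 patients give the same 80.7% power for non-inferiority with a 0.5 mm margin, no true difference and one-sided 0.025. That is correct, and nothing here shows that 50 patients are too few. But the plan states none of those three conditions and uses 0.5 mm for something else, so the coincidence does not supply a margin.

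Second, the 17.7%, 27.2% and 0.68 mm figures matter only if non-significance is read as non-inferiority, which the plan never says; the t-test also yields a confidence interval. This is fair, and those figures show what is at risk under one reading. The interval still has no margin to be compared with.

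Third, the direction can be guessed: the rationale presents two-stage placement as the original protocol, which makes immediate provisionalization the arm on trial. That is a reasonable inference, but it does not reveal which arm was assigned 1.5 mm.

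Fourth, the 2.5% in step 2 is true by definition when the true deficit equals the margin. Agreed; it shows only that one number cannot be both the margin and the expected deficit of the immediate arm.

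Finally, the missing 6-month radiograph is a separate scheduling inconsistency, and the main point stands without it. It matters here because a decision rule must refer to a visit at which the outcome is measured.

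**Conclusion.** The concern holds and must be fixed. The stated objective is non-inferiority; the hypothesis, sample size and analysis are those of a two-sided difference test, and no rule connects them. The fault is an undefined hypothesis and decision rule. It is not an arithmetic error, nor a demonstrated shortfall in patients.

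Whether 50 patients are adequate depends on the missing margin: power ranges from 82.3% at 0.5 mm to 41.0% at 0.3 mm. These figures assume 25 evaluable per arm, SD 0.6 mm at the analysed visit, a true difference of zero and one-sided 0.025. Even at 0.5 mm there is room to lose only two patients before power falls below 80%, and the document gives no dropout allowance beyond the step from 48 to 50.

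**What to change.** Before outcome data are seen, state:

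1. **Direction:** mean bone loss, immediate minus delayed, with immediate as the arm to be shown non-inferior; say which arm was assumed to lose 1.5 mm.
2. **Margin:** a value with its clinical justification. The 0.5 mm is the only difference the plan gives, and it is half of the 1 mm loss assumed in one arm (0.5/1.0), so it needs an argument and should not be adopted by default.
3. **Primary time point:** one visit at which radiographs are taken. Twelve months meets this on the present schedule. Confirm that SD 0.6 mm applies there.
4. **Rule:** non-inferiority is declared only if the upper limit of the two-sided 95% CI for the difference is below the margin; p > 0.05 is not evidence of non-inferiority.
5. **Power:** restated for that test, at a true difference of zero, the chosen margin and the expected evaluable number.

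If a two-sided comparison was intended, remove the non-inferiority label from the title and overview and make no such claim.

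The cost is a rewrite of the statistics section. Enrolment can stay at 50 if a 0.5 mm margin is justified, the other assumptions hold and no more than two patients are lost. A narrower margin or heavier losses mean either a lower stated power or more patients: 74 evaluable at 0.4 mm, 128 at 0.3 mm.

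### Implant survival, a rare yes/no outcome, is assigned the unmatched t-test with no named alternative, and that test is undefined if no implant fails

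*Combined protocol and SAP*

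**What the plan says.** The study design overview lists survival first among the secondary endpoints: "Secondary outcomes will include implant survival". The section on power and statistical analysis gives one method for every primary and secondary outcome: "Differences in the primary and secondary outcomes between the two treatment arms will be calculated using t-test for unmatched samples", with the condition "after checking for data normality". It makes no exception for survival. It does not say what is done if the normality check fails, and it names no method for proportions, no exact test and no time-to-event method. The only other analyses are regression models that add insertion torque to treatment group. Their type is not stated, and they are described as additional, not as a substitute.

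Three other statements bear on the point. Planned enrolment is 50. The section on potential risks says "The overall success of dental implants exceeds 95" per cent. The overview describes the design as follows: "This is a non-inferiority study of 12-month duration comparing the two treatment arms described above".

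**The concern.** A t-test compares means of a roughly continuous measurement. Survival of a single implant is yes/no, and failures should be rare. Two difficulties follow.

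First, the plan's own precondition, the normality check, cannot be satisfied by such data, and the plan does not say what happens next. The analyst would have to pick a method after seeing the failures, and with so few events different reasonable tests give clearly different p-values.

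Second, if nobody loses an implant, the stated test gives no result at all. A report of no failures in either arm can then be read as showing equal survival. In a trial comparing immediate with delayed provisionalization under a non-inferiority label, the useful survival finding is how large a difference the data still allow, and the stated method does not supply it in that case.

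**Working it through.** **The plan's own figure.** The only computed figure is the sample size for bone level. With d = 0.5/0.6 = 0.8333, two-sided alpha 0.05 and power 0.80, the t-test needs 23.6 per arm, so 24 per arm and 48 in total (power 0.807). The stated 48 is reproduced. No calculation is given for survival.

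**Inputs.**
- N = 50 (analysis section).
- Failure rate p below 5% (potential risks section). This is general implant success, not 12-month survival in this trial, so it is a stand-in.
- 25 per arm. No allocation ratio is stated; 1:1 is assumed.
- One implant per participant, read from the singular wording of the eligibility text.

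**Expected failures.** 50 × 0.05 = 2.5 at the 5% bound, and fewer below it. At 5%, the chance of 2 or fewer failures is 54%, and of 5 or fewer 96%.

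**Normality check.** The plan names no test; Shapiro-Wilk is assumed. For 1, 2 or 3 failures among 25, p = 1.2e-10, 7.5e-10 and 3.2e-9. With 0 failures the data are constant and no check can be run.

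**Chance of no failure at all**, (1 − p)^50:

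| Failure rate in both arms | P(0 v 0) |
|---|---|
| 5% (the documents' bound) | 0.95^50 = 7.7% |
| 3% (assumed) | 0.97^50 = 22% |
| 2% (assumed) | 0.98^50 = 36% |

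**The t-test at 0 v 0.** The difference in means is 0 and both variances are 0, so t = 0/0. The pooled and Welch versions both return no statistic and no p-value.

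**What the same data still allow.** The Wilson upper limit for 0/25 is z²/(n + z²) = 3.8415/28.8415 = 0.133. With no failures in either arm, the Newcombe interval for the risk difference is therefore −13.3 to +13.3 points. If the arms were 23 v 27 it would be −12.5 to +14.3, and if 20 v 30, −11.4 to +16.1. The result does not hinge on exact 1:1 allocation.

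**Choice of test with few failures, 4 v 0.**
- t-test: difference 4/25 = 0.16. The variance in the arm with failures is 25 × 0.16 × 0.84/24 = 0.14, so the pooled variance is 0.07. The standard error is √(0.07 × 2/25) = 0.0748, t = 2.14 on 48 df, p = 0.038.
- Fisher's exact test: 2 × C(25,4)/C(50,4) = 2 × 12,650/230,300 = 0.110.

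**Type I error of the t-test** (full enumeration, 0 v 0 counted as no rejection): 0.2%, 2.0% and 4.9% at failure rates of 2%, 5% and 10% in both arms. It does not exceed 5%.

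**The case against.** The strongest reply is that little harm follows. An undefined t-test is visible and cannot by itself support a wrong conclusion; an investigator would simply report 0/25 v 0/25, and any reader could derive the interval from those counts. The phrase "after checking for data normality" implies that something else would be used if the check failed. Survival is one of several secondary outcomes, with no margin and no decision rule. The t-test is also not a bad test here: its type I error is controlled, and at failure rates of 5% v 15% its power is 21% against 7% for Fisher's test.

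Much of this stands, and it is why the point is minor and why Fisher's test is not offered as the main replacement. It does not remove the point. A condition with no stated alternative leaves the method to be chosen after the data are seen, and for this outcome the condition is certain to fail.

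A reader might infer three stronger claims that the documents do not support.
- That a trial with no failures is quite likely. At the only bound the documents give, 5%, the chance is 7.7%; the higher figures need lower rates that the wording permits but does not state.
- That the plan would publish a falsely precise, zero-width interval. The plan names no confidence interval. Scoring an undefined result as an interval from 0 to 0 would be the reader's construction.
- That lost implants bias the bone-level comparison. How they enter that comparison is a separate question about the primary outcome, and the size of any effect cannot be derived from the documents.

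**Conclusion.** The point holds, at minor severity. The stated method does not fit implant survival: its precondition cannot be met with about 2.5 or fewer expected failures among 50, no alternative is named, and with no failures it yields nothing, although differences of about 13 points either way are not excluded. The conclusion that the test misfits the outcome rests only on survival being yes/no, which is the natural reading because the plan does not define it; a time-to-event reading would not suit a t-test either. The sizes rest on general success standing in for survival, one implant per participant and 25 per arm. The finding is not that false positives are inflated, and it does not touch the sample size or the primary analysis.

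**What to change.** Exclude survival from the t-test sentence and add, for example: *Implants failed by 12 months will be reported as counts per arm, with a Newcombe (score-based) 95% confidence interval for the difference in failure risk as the main survival result.* Newcombe is one suitable choice; another score-based interval would also serve if named in advance. An exact p-value is optional and secondary. The horizon fits the existing schedule: "The 12-month examination will conclude the study visits".

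The cost is one or two sentences and a few lines of analysis code, with no new data or visits. The downside is a wider, conservative interval. At 5% failure in both arms its mean width is about 32 points, against 23 for the interval that would accompany the t-test. The 23 counts the no-failure result as zero width. With that result set aside the comparison is (0.325 − 0.077 × 0.266)/0.923 = 0.33 against 0.231/0.923 = 0.25, or about 33 v 25 points.
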